11.1.3 Follow up of adverse events

An AE should be followed until it has resolved, has a stable sequelae, the Investigator determines that it is no longer clinically significant, or the subject is lost to follow up.

If an AE is ongoing at the end of the study for a subject, follow up should be provided until resolution/stable level of sequelae is achieved, or until the Investigator no longer deems that it is clinically significant, or until the subject is lost to follow up. If no follow up is provided, the Investigator must provide a justification. The follow up will usually be continued for 30 days after the subject has discontinued his/her IMP.

Information on SAEs obtained after final clinical database lock will be captured through the Patient Safety (PS) database without limitation of time.

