At Visit 4 (at the end of the Stabilization Period), subjects will enter a 12-week Maintenance Period during which they will receive their target dose (or their fallback dose, if applicable). During the entire 12-week Maintenance Period, the dose of IMP (target dose or fallback dose) and concomitant AEDs must remain stable. Subjects must return to the clinic for scheduled visits as outlined in [Table 2-1](#).

Subjects who complete the Maintenance Period will return for an End of Treatment Visit. Subjects who discontinue early from the study will return for an Early Discontinuation Visit (EDV). Subjects completing the Maintenance Period will have the opportunity to enroll into the OLE study, EP0093. They will be converted to the entry dose of the EP0093 study, 400mg/day. Subjects withdrawing from the study or deciding not to participate in the OLE study (EP0093) will be progressively tapered off the IMP.

For subjects discontinuing the study:

Taper Period (4 weeks)

The 4-week Taper Period will be required for subjects who choose not to enroll in the OLE study or who discontinue prior to the end of the Maintenance Period. Subjects participating in the 4-week Taper Period should be gradually tapered off the IMP over a 3-week period followed by 1-week drug-free period. A faster or slower taper schedule than the suggested 3 weeks may be implemented, if medically necessary, as per the Investigator's medical judgement. Subjects will start their taper at the EDV/End-of-Treatment (Visit 7) and will return 1 week after last intake of IMP for the End-of-Taper Visit at Visit 8. Changes to concomitant AED(s) are not allowed

during the taper of PSL unless they are medically necessary as per the Investigator's medical judgement to treat rebound seizures.

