#### Safety Follow-Up Period

Safety follow up for subjects not entering the OLE will consist of 1 required visit, 30 days after the last IMP intake (Week 23 or sooner in case of early discontinuation) including an echocardiogram. An additional follow-up echocardiogram will be performed at 6 months ( $\pm 1$  month) after the last IMP intake only for subjects exposed to IMP for more than 3 weeks.

For subjects continuing to the OLE study:

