k An echocardiogram will also be performed 6 months after last IMP intake for subjects exposed to >3 weeks to IMP and discontinuing the study (but not for subjects with <3 weeks exposure).

l AED samples will ideally be taken immediately prior to dose of concomitant medication on each occasion. If this is not possible, then the sample may be taken at any time after dose and the timing of sample in relation to dose should be kept the same ( $\pm 1$  hour) on each occasion for each subject. Therefore, the timing of visits for each subject when AED samples are collected should be scheduled approximately at the same time whenever possible. Assay of parent PSL and metabolites may be included in the AED panel of tests at Visits 6 and 7.

m On Visits 6 and 7, unless the concomitant AED sample is within  $\pm 5$  minutes of a scheduled MITRA sample for PSL assay, a separate, additional MITRA sample will be taken at same time as the concomitant AED blood sample.

n Subjects are requested to provide blood samples for measurement of PSL and metabolites whenever possible. On Visits 3, 5, and 6, site personnel should obtain blood samples for measurement of random PSL concentrations at any time between IMP intake and record accurately the time of last IMP intake and the time of sample collection. On Visits 4 and 7, blood samples for measurement of sparse PK profiles will be collected as follows: immediately before IMP intake

---

(maximum 15 minutes before intake) and then 3 times after (between 30 minutes and 3 hours after IMP intake), taken at least 30 minutes apart. All samples may be taken either at home or in the site or partly at home and partly at the site.

o For all female subjects, serum pregnancy test at Visits 1 and 7 (in case the subject enters into the OLE study) and where applicable, Urine pregnancy test will be used at other visits for female subjects of childbearing potential.

p Seizure counts are collected on the subject's daily record card on a daily basis.

[figure not shown]
q At each visit following an IMP dispensation, IMP should be presented to check for compliance.

r Subject entry interview will be performed on a voluntary basis either at Visit 1 or Visit 2. Subject/caregiver exit interview/survey will be performed on a voluntary basis either at Visit 6 or Visit 7.

s The SFU Visit will be performed only for subjects who do not enter EP0093.

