## 3 DATA ANALYSIS CONSIDERATIONS

### 3.1 General presentation of summaries and analyses

Statistical analysis and generation of tables, figures, subject data listings, and statistical output will be performed using SAS Version 9.3 or higher. All tables and listings will use Courier New font size 9.

Descriptive statistics will be displayed to provide an overview of the study results. For categorical variables, the number and percentage of subjects in each category will be presented. Unless otherwise noted, all percentages will be displayed to 1 decimal place. No percentage will be displayed for zero counts, and no decimal will be presented when the percentage is 100%. For continuous variables, descriptive statistics will include number of subjects with available measurements (n), mean, SD, median, minimum, and maximum.

Decimal places for descriptive statistics will always apply the following rules:

- “n” will be an integer
- Mean, SD, and median will use one additional decimal place compared to the original data
- Minimum and maximum will have the same number of decimal places as the original value.

Unless otherwise specified, statistical tests of efficacy variables will be presented as two-sided p values rounded to three decimal places. P-values less than 0.001 will be presented as “<0.001” and p-values greater than 0.999 will be presented as “>0.999.” Statistical comparisons will be two-sided and will be performed at the 0.05 level of significance.

A complete set of data listings containing all documented data as well as calculated data (e.g., change from Baseline), as applicable, will be generated.

Treatment groups will be displayed as: Placebo, PSL 50 mg bid, PSL 100mg bid, PSL 200mg bid, and PSL 400mg bid.

Log-transformation is based on natural logarithm. For analyses on log-transformed values, model estimates will be back-transformed to anti-log space for table presentation. See Section 8.1.1 for details.

Data collected at scheduled visits will be included the by-visit summary. Data collected at unscheduled visits will not be included in the by-visit summary, but will be considered when determining the Last Visit, minimum, and maximum post-Baseline values during the Treatment Period. Data collected on Visit 8 will be summarized separately for subjects in the Conversion Period versus the Taper and Safety FU Period.

In general, all CRF data will be presented in the subject listings.

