**Table 3–1: Start and end of EP0091 analysis periods**

Analysis Period			Details
Description	Start	End	
Baseline (Week -4)	Date of informed consent at Visit 1	Date of the day before the date of Visit 2.	This is an approximate 28-day period for calculation of Baseline seizure frequencies. Study drug is dispensed, and first dose is generally taken the day of the Baseline Visit (Visit 2, Day 1). Note the pre-dose assessments will also be included in the Baseline Period.
Titration and Stabilization*	The date of the Baseline Visit, (Visit 2, Day 1).	The date of the day before Visit 4 or the end of the treatment period if the subject has discontinued prior to Visit 4.	For evaluation purposes, if results are presented by analysis period, the Titration and the Stabilization interval will be considered together (approximately 4 weeks in total). Titration is a period of dose increases to reach the protocol specified dose. Stabilization is an approximate week-long interval to stabilize at the target dose level. During stabilization the dose may be adjusted once (i.e. to a fallback dose).
Maintenance*	The date of Visit 4.	The date of Visit 7 or the end of the treatment period if the subject has discontinued prior to Visit 7.	This is a 12-week period where the subject remains on the randomized target dose (or fallback dose, if applicable).
16-week Treatment Period*	The date of the Baseline visit (Visit 2)	The date of Visit 7 or the end of the treatment period if the subject has discontinued prior to Visit 7.	Titration and Stabilization Period and Maintenance Period combined.
Conversion	The date of the day after Visit 7	The date of Visit 8.	This is a 3-week period of dose conversion to enable the subjects to enroll into the OLE study EP0093.
Taper and Safety Follow-up	The date of the day after Visit 7/EDV or the date of day after Visit 8 if the subject tapered after conversion	The date of final contact.	Subjects who withdraw from the study or decide not to participate in the OLE study will be tapered off the IMP during a 3-week period followed by a 1-week drug-free period. A SFU visit will be performed 30 days after the last IMP intake.

OLE=open-label extension; SFU=Safety Follow Up

\* Only seizure data prior to and on the date of last dose of study medication will be included in the analysis.

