- Summary of the duration in days per event for the following TEAEs: somnolence, dizziness, fatigue, irritability and headache. In this analysis, if an AE is ongoing, the duration will be calculated till the date of final contact.

Summaries will be presented based on standard Sponsor AE table formats and considering formats used for the PSL program.

Where dates are missing or partially missing, AEs will be assumed to be treatment-emergent, unless there is unmistakable evidence (through comparison of partial dates, see Section 4.2) to suggest that the AE started prior to the first dose of study treatment. Summary tables will contain counts of subjects, percentages of subjects in parentheses and the number of events where applicable. A subject who has multiple events in the same MedDRA category (SOC or PT) will be counted only once in the subject count for that category, however all events will be included in the event count for the category. In summaries including relationship to study treatment, the following relationships will be summarized: 'Not related', 'Related'. A subject may be counted more than once according to the relationship to study treatment. Events with missing relationship will be considered as 'Related' to the last given study product for summary purposes but recorded as missing in the listings. In summaries of the maximum intensity, the following intensity categories will be summarized: 'Mild', 'Moderate', 'Severe'. Subjects who experience the same event multiple times, with differing severities, will be included in the most severe category. Events with missing intensity will be considered as 'Severe' events for summary purposes but recorded as missing in the listings. The main reasons for treatment discontinuation will be listed by subject. The daily dose of study medication corresponding to the AE onset date will be included in the listing. Daily dose will be derived from 'Study Medication Administration' CRF.

Adverse event summaries will be ordered in terms of decreasing frequency for SOC, and PT within SOC, within the PSL total group column.

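### The adverse-event duration table in SAP 10.2 enters events still ongoing at final contact as complete, so its mean and maximum are too short by an amount set by follow-up

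*SAP*

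**What the plan says.** Among the outputs for TEAEs in the overall Treatment Period, SAP 10.2 lists a "Summary of the duration in days per event for the following TEAEs: somnolence, dizziness, fatigue, irritability and headache". The rule for unresolved events follows directly: "if an AE is ongoing, the duration will be calculated till the date of final contact".

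SAP 10.2 names no statistics for this table, so the general rule of SAP 3.1 applies: "For continuous variables, descriptive statistics will include number of subjects with available measurements (n), mean, SD, median, minimum, and maximum". Nothing in 10.2 marks the cut-off durations as lower bounds, counts them in this table, or censors them.

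The date of final contact depends on the subject's path.

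- **Not entering the extension.** SAP 2.6.1 says "Safety follow up for subjects not entering the OLE will consist of 1 required visit, 30 days after the last IMP intake", which it places at Week 23, or sooner after early discontinuation. Table 3-1 adds "Subjects who withdraw from the study or decide not to participate in the OLE study will be tapered off the IMP", and ends that period at final contact.
- **Entering the extension.** A footnote to SAP Table 2-1 says "The SFU Visit will be performed only for subjects who do not enter EP0093". Protocol 8.3.2 puts study termination for these subjects at Visit 8, at Week 19.

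Protocol 11.1.3 asks that adverse events be followed until resolved, stable or no longer clinically significant, but adds: "The follow up will usually be continued for 30 days after the subject has discontinued his/her IMP".

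**The concern.** An event that has not resolved at last contact has a duration known only to exceed the recorded value. Averaging such values with completed ones pulls the mean down, and the pull is strongest when events persist. The cut-off also varies between subjects, so the same unresolved event is given a different length according to how the subject left the study.

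The five terms were the most frequently reported TEAEs in the earlier proof-of-concept study (Protocol 2.3.1), and safety and tolerability against placebo is the secondary objective. A short mean duration in this table could be read as showing that these events pass quickly when part of it reflects only the end of observation.

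There is a second complication. The events are those of the Treatment Period, but the clock runs on to final contact and so through Conversion or Taper, when treatment changes. Placebo subjects who convert start to receive padsevonil.

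**Working it through.** The plan gives no figure for event duration or for the number of events left ongoing, so there is nothing to reproduce. What can be checked is how far follow-up alone moves the entry, and what that does to the mean under an assumed distribution.

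**Step 1: days available from onset to final contact.** Visit weeks are from the schedule of assessments. For early discontinuation, the inputs are a subject "gradually tapered off the IMP over a 3-week period" and a final visit 30 days after last intake. Onset on Day 7 and stopping at Week 2 are assumptions. Days available C = day of final contact − 7 + 1.

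- Extension entrant, Week 19: 19 × 7 = 133, so C = 127.
- Tapering completer, Week 23: 23 × 7 = 161, so C = 155.
- Stop at Week 2: 14 + 21 + 30 = 65, so C = 59.

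The same unresolved event is entered as 127, 155 or 59 days, a spread of 155 − 59 = 96 days from follow-up alone.

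**Step 2: effect on the mean.** Assume exponential true durations with mean μ. The share still ongoing is exp(−C/μ), and the mean reported under the SAP rule is μ(1 − exp(−C/μ)).

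For a true median of 60 days, μ = 60/ln 2 = 86.6.

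- C = 127: exp(−127/86.6) = 0.23 ongoing. Reported mean 86.6 × 0.77 = 67 days, 23% short.
- C = 155: exp(−155/86.6) = 0.17 ongoing. Reported mean 86.6 × 0.83 = 72 days, 17% short.
- C = 59: exp(−59/86.6) = 0.51 ongoing. Reported mean 86.6 × 0.49 = 43 days, about half the truth.

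The same formula over a range of true means gives these reported means, in days:

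| True mean | C = 59 | C = 127 | C = 155 |
|---|---|---|---|
| 14 | 13.8 | 14.0 | 14.0 |
| 30 | 25.8 | 29.6 | 29.8 |
| 60 | 37.6 | 52.8 | 55.5 |
| 120 | 46.6 | 78.4 | 87.0 |
| 240 | 52.3 | 98.6 | 114.2 |

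The shortfall runs from almost nothing to 78% (52.3 against 240).

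**Step 3: effect on the median.** With a common C, the reported median is the smaller of the true median and C. For a true median of 60 days it is correct at C = 127 and C = 155, and is 59 at C = 59. For a true mean of 240 days (median 240 × ln 2 = 166) it is wrong on all three paths: 127, 155 and 59.

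**Step 4: comparison within the SAP.** For time to return to the Baseline seizure count (SAP 8.3.2.22), subjects without the event are censored and Kaplan-Meier is used. SAP 4.2.2.2 leaves a completely unknown stop date unimputed. The duration table follows neither practice.

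**The case against.** The case for leaving the rule alone has real substance.

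- This is one descriptive table among many. Event duration is not among the primary or other safety variables in SAP 2.4, and no hypothesis test depends on it. This stands, and it makes the point minor.
- The median is reported beside the mean and is often correct. This stands when fewer than half the events are ongoing and they are cut off beyond the true median. It does not rescue the mean or maximum.
- Protocol 11.1.3 asks for follow-up to resolution or stability, with a justification if none is given, and SAP 4.2.2 lists stop dates as reported, so ongoing events remain identifiable. Both reduce the problem. But follow-up is usually limited to 30 days after treatment stops, extension entrants leave at Visit 8, and a listing does not correct the summary.
- Kaplan-Meier is not beyond criticism. Subjects may leave because of these same events, so censoring may be informative, and one subject can contribute several events. This stands, and is why the count of ongoing events must be shown as well.

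A reader might also infer more than the documents support: that every duration is understated, that the table was designed to show these events are transient, or that the arms are known not to be comparable. Resolved events are measured correctly. No purpose is stated for the table. No dropout or extension-entry rates by arm are given, so non-comparability is only a possibility.

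**Conclusion.** The point holds in a limited form. For events unresolved at final contact, the plan enters lower bounds as complete durations. When such events occur, the reported mean is too short, and so is the maximum if the longest event is among them. The median is affected only if about half or more of the events are ongoing, or if some are cut off before the true median.

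The actual size cannot be computed, because the number of ongoing events and the distribution of durations are not given. The illustrative means of about 67 and 72 days against 87 rest on exponential durations, a true median of 60 days and onset on Day 7. Later onset or early discontinuation makes the shortfall larger; short-lived events make it negligible. Week 19 as final contact for extension entrants is inferred from their study termination at Visit 8.

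This is a minor fault in a descriptive safety output. Sample size, power and Type I error are untouched.

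**What to change.** Amend SAP 10.2 so that, for each of the five terms and each arm, the table gives:

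1. the number and percentage of events ongoing at final contact;
2. the Kaplan-Meier median and quartiles of duration, with ongoing events censored.

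Two details need stating.

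- **One censoring rule for all arms.** Either the end of the Treatment Period (the start of Conversion or Taper) or final contact would serve, if applied to everyone. The first keeps days on changed treatment out of the estimate; the second uses all follow-up. Censoring only placebo subjects at Conversion would create arm-dependent follow-up, since Protocol Table 7-4 shows that most padsevonil arms change dose then too. If the earlier date is chosen, give the number ongoing at that date as well.
- **Worsening events.** Protocol 11.1.2.2 closes an event that increases in intensity, with worsening as its outcome, and opens a repeat record. Link the two, so that the closure does not count as resolution.

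The cost is a few SAP sentences and one revised table shell. It needs no new data and uses a method already in the SAP. The table becomes slightly more complex, and Kaplan-Meier assumes non-informative censoring, so the ongoing count should stay beside the estimates.

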### **10.3 Clinical laboratory evaluations**

Clinical laboratory hematology, chemistry and urinalysis measurements obtained from blood/urine samples collected throughout the study are presented in Table 10-1.

During the study, non-protocol-specified lab parameters (unplanned) may be collected. Summaries of lab parameters will only include planned parameters as specified in the protocol. All lab parameter values will be listed and summarized using international units.

The observed value and change from Baseline will be summarized descriptively by treatment group and PSL total group and scheduled study visit. The Last Visit, minimum, and maximum post-baseline values during the Treatment Period will also be included. These summaries will be organized by lab function panel and parameter.

Shift from Baseline to the maximum and minimal values during the Treatment Period based on normal range (Low, Normal, High) will be provided for hematology and blood chemistry parameters in Table 10-1.

Possibly clinically significant treatment-emergent (PCST) criteria have been developed based on FDA Division of Neuropharmacologic Drug Products guidelines with some UCB-defined additions and are provided in Appendix 13.1. For lab parameters with PCST criteria, the number and percentage of subjects with a PCST value at any time (scheduled and unscheduled visits) during the Treatment Period will be summarized by treatment group and PSL total group. . Treatment-emergent values are those occurring any time on or after the first dose of study medication in EP0091. Subject numbers for those meeting the PCST criteria will also be presented.

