13.4 Planned safety and other analyses

13.4.1 Safety analyses

Adverse events will be coded using the Medical Dictionary for Regulatory Activities (MedDRA[®]). Adverse events will be summarized by MedDRA system organ class and preferred term. The incidence of SAEs, AEs leading to premature discontinuation or dose tapering, and related AEs, and the incidence of AEs by maximum intensity, will also be summarized.

Laboratory values, ECG data (ventricular rate, PR, QTcB, QTcF, and QRS) and arrhythmias, vital signs, weight, and changes from Baseline in these measures will be summarized by period, visit, and treatment group. Possibly clinically significant treatment emergent abnormalities for laboratory values, vital signs, and weight will be listed and summarized by period and visit for each treatment group.

Electrocardiogram abnormalities as well as physical and neurological abnormalities will also be listed by period and visit. Quantitative safety parameters will be summarized descriptively by time point and treatment group. Categorical safety summaries will provide the number and percentage of subjects within each summarized category.

Doppler echocardiogram results at Baseline and during and after treatment, and changes from Baseline, will be listed and descriptively summarized.

All C-SSRS data obtained at Baseline and subsequent visits will be reported as a listing ordered by subject and visit. Psychiatric and Mental Status assessment and CIWA-B data will also be included using listings.

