### **3.2.2.2 End of the 16-week treatment period**

The end of the 16-week overall treatment period will be either the date of Visit 7 for subjects completing the Treatment Period, or the date of the early discontinuation visit (EDV), for subjects who discontinued during the Treatment Period. If a subject does not have a Visit 7/EDV, then the date of the final contact will define the end date of the Treatment Period.

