### **3.2.3 Analysis periods**

The start and end dates of each analysis period (following the study design) are used for the classification of efficacy and safety data. The exact start and end of each of these periods is described for calculation purposes in Table 3–1. Note that measurements obtained from diaries returned on the start date of the Titration and Stabilization Period would be included in the Baseline Period calculations. Refer to Section 3.3.1. Similarly, measurements from diaries returned on the start date of a subsequent period would be included in calculations for the previous period.

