### **3.9 Changes to protocol-defined analyses**

Not applicable; there have not been any changed to protocol defined analyses.

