## 10.4 Vital signs, physical findings, and other observations related to safety

### 10.4.1 Vital Signs

Vital measurements (including SBP, DBP, PR, RR and weight) are generally collected in standard units. If any measurements are collected in international units, they will be converted to standard units for summaries. Subject Listings will be prepared for vitals variables.

The observed value and change from Baseline will be summarized descriptively by treatment group and scheduled study visit. In the same table, the observed value and change from Baseline

will be summarized by treatment for all scheduled visits. The Last Visit, minimum, and maximum post-baseline values during the Treatment Period will also be included.

The number and percentages of subjects with abnormal vital signs and body weight during the Treatment Period will be presented by treatment group and PSL total group. The abnormal vital sign and body weight criteria are provided in Appendix 13.2. Subject numbers for those meeting abnormal criteria will also be presented.

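### SAP 10.3 and 10.4.1 reduce the by-period and by-visit abnormality summaries promised in Protocol 13.4.1 to one Treatment Period count per data type, and SAP 3.9 does not declare the change

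*SAP*

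**What the plan says.** Protocol 13.4.1 states that possibly clinically significant treatment-emergent "abnormalities for laboratory values, vital signs, and weight will be listed and summarized by period and visit for each treatment group".

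SAP 10.3 plans, for labs, that the number and percentage of subjects "with a PCST value at any time (scheduled and unscheduled visits) during the Treatment Period will be summarized", and adds: "Subject numbers for those meeting the PCST criteria will also be presented". For vital signs and weight, SAP 10.4.1 says: "The number and percentages of subjects with abnormal vital signs and body weight during the Treatment Period will be presented". Neither section splits these counts by period or by visit. The by-visit tables in both sections cover observed values and change from Baseline.

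SAP Table 3–1 describes the 16-week Treatment Period as "Titration and Stabilization Period and Maintenance Period combined". On its end date, SAP 3.2.2.2 says: "The end of the 16-week overall treatment period will be either the date of Visit 7 for subjects completing the Treatment Period"; for those who discontinue, it is the early discontinuation visit. Conversion and Taper and Safety Follow-up are separate periods in the same table, and SAP 3.2.3 says that the period dates "are used for the classification of efficacy and safety data".

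SAP 3.9 states that "there have not been any changed to protocol defined analyses". SAP 1 names Protocol Amendment 2 as its basis, which is the protocol version at hand.

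**The concern.** The protocol promises two breakdowns of the abnormality counts. The SAP delivers neither a visit-level count nor any period-level count beyond the pooled Treatment Period, and its section on changes says there are none. The general clause in SAP 1, that the protocol governs unless the SAP specifies otherwise, does not restore the missing tables, because 10.3 and 10.4.1 do specify otherwise.

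The practical effect falls after Visit 7. Dosing continues for about 3 more weeks, in Conversion or Taper. In Conversion, former placebo subjects take padsevonil for the first time in this study (Protocol 7.2.3). For those who taper, Visit 8 comes 1 week after last intake (Protocol 5.1), when rebound or withdrawal effects might show. SAP 10.3 defines treatment-emergent lab values as any from the first dose onward, so post-dose lab values at Visits 8 and 9 meet the SAP's own definition yet fall outside its PCST count.

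**Working it through.** The plan gives no figure to reproduce. The check sets the scheduled collections against the period covered by the count.

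**Inputs.** Visits from Protocol Table 5-1 (repeated as SAP Table 2-1); period limits from SAP Table 3–1. A subject entering EP0093 ends at Visit 8; a tapering subject also has Visit 9.

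| Data type | Inside Treatment Period | After it | Outside, entering EP0093 | Outside, tapering |
|---|---|---|---|---|
| Labs | V4, V6, V7 (3) | V8, V9 | 1/(3+1) = 25% | 2/(3+2) = 40% |
| Vital signs | V3 to V7 (5) | V8, V9 | 1/(5+1) = 17% | 2/(5+2) = 29% |
| Weight | V4 to V7 (4) | V8, V9 | 1/(4+1) = 20% | 2/(4+2) = 33% |

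These shares are for subjects who complete Maintenance.

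**By visit.** With one count per data type at each scheduled post-baseline visit, the protocol commitment amounts to 5 + 7 + 6 = 18 visit-level counts. The SAP plans none.

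**By period.** The Treatment Period is itself one of the SAP's periods, so one period-level summary is planned per data type, 3 in all. None is planned for Titration/Stabilization, Maintenance, Conversion or Taper/Safety Follow-up separately.

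**What a split inside the Treatment Period would add.** Table 3–1 starts Maintenance on the date of Visit 4. Titration/Stabilization then holds 0 of 3 scheduled lab collections, 0 of 4 weight collections and 1 of 5 vital-sign collections (V3). If Visit 4 were counted there, the figures would be 1 of 3, 1 of 4 and 2 of 5.

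**Where a crossing first seen at Visit 8 or 9 would appear.**
- Potential Hy's Law: the table in SAP 10.3.1 states no period limit, so it can include these cases.
- Liver values meeting PDILI criteria: Protocol 11.2.1 requires them to be reported as AEs, and SAP 10.2 tabulates TEAEs by period, including Conversion and Taper/Safety Follow-up. The PDILI summary table itself is limited to the Treatment Period.
- Everything else: by-visit descriptive statistics, which include minimum and maximum (SAP 3.1), listings, the subject numbers for lab PCST, or an AE that depends on the Investigator's judgment (Protocol 11.3.1 for vital signs).

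**Likely effect on overall incidence (illustration).** Assume constant weekly risk over the maximum 19 weeks of exposure, of which 16 are counted. A total risk p is then tabulated as 1 − (1 − p)^(16/19).
- p = 2%: 1 − 0.98^(16/19) = 1.69%; difference per 80 subjects = 80 × (2.00% − 1.69%) = 0.25.
- p = 5%: 1 − 0.95^(16/19) = 4.23%; difference per 80 subjects = 80 × (5.00% − 4.23%) = 0.62.

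The 2% and 5% are assumed; the documents give no crossing rates.

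**The case against.** The strongest defence is that little is lost. Protocol 4.2.2 names changes in lab and vital-sign parameters as safety variables, not threshold counts. Protocol 13.4.1 does not say which periods it means, and the TEAE periods listed in 4.2.2 include Taper but not Conversion. The subject-number sentence in SAP 10.3 names no period and, read with the first-dose definition, could identify late lab cases. By-visit minima and maxima show whether anyone passed a fixed limit. Conversion has no concurrent placebo group, so its counts can only be descriptive.

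Much of this stands, and it limits the size of the point. It does not remove it. A by-visit commitment covers Visits 8 and 9 whatever the periods are. Extremes do not show how many subjects crossed, and an identifier list is not a count by visit or period. The SAP also already uses the missing formats: TEAEs by period (10.2), overall ECG result and QTc classes by visit (10.4.2), psychiatric abnormalities by visit (10.4.4.3), and Visit 8 data split by Conversion versus Taper/Safety Follow-up (3.1).

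A reader might infer three stronger things that the documents do not support:
- That former placebo subjects' first padsevonil exposure escapes every abnormality count. The ECG and psychiatric counts are by visit, and both assessments are scheduled at Visit 8.
- That the randomized safety comparison is biased. The Treatment Period count is the right basis for that comparison and is planned.
- That the number of affected placebo subjects can be projected by applying the earlier Phase 2 rollover of 42 of 55 to 80 subjects (about 61). Those subjects were all already on open-label padsevonil before rollover, so the analogy is weak.

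**Conclusion.** The point holds as an undeclared narrowing of the descriptive safety tables. The SAP plans one Treatment Period count for each of labs, vital signs and weight where the protocol promised summaries by period and visit, and SAP 3.9 is inaccurate in saying that nothing changed. Lab, vital-sign and weight thresholds first crossed at Visit 8 or 9 enter no planned PCST or abnormality count, apart from potential Hy's Law cases; liver values meeting PDILI criteria still reach the AE tables. The part that matters most is Visit 8 for placebo subjects who convert, because it is their only scheduled on-drug lab, vital-sign and weight collection in EP0091.

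Efficacy and the randomized safety comparison are untouched. Under the constant-risk assumption, the effect on overall incidence is under one subject per 80. This should be corrected, but it does not threaten the trial's conclusions. The reading of the texts is firm; only the incidence illustration rests on assumptions.

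**What to change.** Keep the Treatment Period count as the randomized comparison. Add to SAP 10.3 and 10.4.1, with subjects assessed as denominator:
- counts of lab PCST values and of abnormal vital signs and weight by scheduled visit, including Visits 8 and 9;
- the same counts by period, at least for Conversion and for Taper/Safety Follow-up. Show Conversion by prior arm, so that former placebo subjects can be identified, and label it descriptive because all arms move toward 400mg/day.

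If Titration/Stabilization and Maintenance are also separated, state which of them Visit 4 belongs to; otherwise the first has no scheduled lab or weight data.

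If the sponsor prefers a narrower presentation, SAP 3.9 should declare it as a change from Protocol 13.4.1 and give the reason.

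The cost is SAP wording and a few repeated table programs on data already collected and periods already defined. The downside is a few more descriptive tables. Declaring the change instead costs one sentence.
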